#### **Section 7.3.1 of the CTP:**

*For study part 1 and part 2, point estimates for the ratios of the geometric means (test/reference) for the primary endpoints [...] and their two-sided 90% confidence intervals (CIs) will be provided.*

*For each endpoint, the difference between the expected means for log(T)-log(R) will be estimated by the difference in the corresponding adjusted means (Least Squares Means). Additionally their two-sided 90% confidence intervals will be calculated based on the residual error from the ANOVA and quantiles from the t-distribution. These quantities will then be back-transformed to the original scale to provide the point estimate and 90% CIs for each endpoint.*

#### Exclusion of plasma concentrations

The ADS ADPC (PK concentrations per time-point or per time-interval) contains column variables ACEXC or ACEXCO indicating inclusion/exclusion (ACEXC) of a concentration and an analysis flag comment (ACEXCO). Exclusion of a concentration depends on the analysis flag comment ACEXCO. For example, if ACEXCO is set to “ALL CALC”, the value will be excluded for all types of analyses based on concentrations. If ACEXCO is set to “DESC STATS” the value will be excluded from descriptive evaluations per planned time point/time interval. If ACEXCO contains the addition “TIME VIOLATION” or “TIME DEVIATION”, the value can be used for further analyses based on actual times. If ACEXCO is set to “HALF LIFE”, the value will be excluded from half-life calculation only; the value is included for all other analyses. Excluded concentration itself will be listed in the CTR associated with an appropriate flag.

#### Exclusion of PK parameters

The ADS ADPP contains column variables APEXC and APEXCO indicating inclusion/exclusion (APEXC) of a PK parameter and an analysis flag comment (APEXCO). All analyses based on the PKS are based on PK parameter values which are not flagged for exclusion, i.e. with APEXC equal to “Included”.

Further details are given in “Noncompartmental Pharmacokinetic / Pharmacodynamic Analyses of Clinical Studies” (4) and “Description of Analytical Transfer Files and PK/PD Data Files” (5).

## **7.5           SECONDARY ENDPOINTS**

### **7.5.1       Key secondary endpoint**

This section is not applicable as no key secondary endpoint has been specified in the protocol.

### **7.5.2       Secondary endpoints**

The analysis of secondary endpoints will be based on the PKS.

The secondary endpoints will be statistically analysed in the same way as for the primary endpoints.

See [Section 7.4](#) of this TSAP for details regarding exclusion of PK parameters and plasma concentrations.

## 7.6.2 Safety parameters

Safety endpoints and tolerability will be analysed as described in [Section 7.8](#) of this TSAP.

## 7.7 EXTENT OF EXPOSURE

Descriptive statistics are planned for this section of the report.

## 7.8 SAFETY ANALYSIS

All safety analyses will be performed on the TS.

### 7.8.1 Adverse Events

AEs will be coded with the most recent version of MedDRA.

The analyses of AEs will be descriptive in nature. All analyses of AEs will be based on the number of subjects with AEs and not on the number of AEs.

For further details on summarization of AE data, please refer to "Analysis and Presentation of Adverse Event Data from Clinical Trials" ([7](#)) and "Handling of missing and incomplete AE dates" ([3](#)).

The analysis of AEs will be based on the concept of treatment emergent AEs. That means that all AEs will be assigned to screening, on-treatment or follow-up phases as defined in [Section 6.1](#). AEs will be analysed based on actual treatments, as defined in [Table 6.1: 1](#).

An overall summary of AEs will be presented. This overall summary will comprise summary statistics for the class of AESIs.

**CTP Section 5.2.6.1.4:** *The following are considered as AESIs:*

- Hepatic injury  
*A hepatic injury is defined by the following alterations of hepatic laboratory parameters:*
  - *An elevation of AST (aspartate transaminase) and/or ALT (alanine transaminase)  $\geq 3$ -fold ULN combined with an elevation of total bilirubin  $\geq 2$ -fold ULN measured in the same blood sample, or*
  - *Aminotransferase (ALT, and/or AST) elevations  $\geq 10$  fold ULN*

The investigator had to classify on the eCRF whether an observed AE was an AESI or not.

According to ICH E3 ([8](#)), in addition to deaths and SAEs, "other significant" AEs need to be listed in the clinical trial report. These will be any non-serious adverse event that led to an action taken with study drug (e.g. discontinuation or dose reduced or interrupted).

An overall summary of adverse events will be presented.

The frequency of subjects with AEs will be summarised by treatment, primary SOC and preferred term. AEs which were considered by the investigator to be drug related will be

summarised separately. Separate tables will also be provided for subjects with SAEs and subjects with AESIs. AEs will also be summarized by maximum intensity.

The SOCs and preferred terms within SOCs will be sorted by descending frequency over all treatment groups.

For disclosure of AE data on ClinicalTrials.gov, the frequency of subjects with non-serious AEs occurring with an incidence of greater than 5 % (in preferred terms) will be summarised by treatment, primary SOC and preferred term. The frequency of subjects with SAEs will also be summarised.

For disclosure of AE data in the EudraCT register, the frequency of AEs, the frequency of non-serious AEs with an incidence of greater than 5 % (in preferred terms) and the frequency of SAEs will be summarized.

For support of lay summaries, the frequency of subjects with drug-related SAEs will be summarized by treatment, primary SOC and preferred term.

If the subject reports headaches during the treatment period further information about the duration of headache, location, characteristics, and signs and symptoms were recorded. The information will be summarized with descriptive statistics.

### **7.8.2      Laboratory data**

The analyses of laboratory data will be descriptive in nature and will be based on BI standards "Display and Analysis of Laboratory Data" ([9](#)).

Analyses will be based on normalised values, which mean transforming to a standard unit and a standard reference range. The original values will be analysed if the transformation into standard unit is not possible for a parameter.

Descriptive statistics of absolute values and change from baseline from laboratory parameters over time (see [Section 6.7](#)) will be provided. Frequency tables of changes between baseline and last value on treatment with respect to the reference range will be presented.

Unscheduled measurements of laboratory data will be assumed to be repeat measurements of the most recent scheduled measurement (e.g. for follow-up or confirmation of a particular value). Therefore, unscheduled measurements will be assigned to the planned time point of the previous scheduled measurement. Descriptive statistics will be calculated by planned time point based on the worst value of the subject at that planned time point (or assigned to that planned time point).

Possibly clinically significant abnormal laboratory values are only those identified either in the Investigator's comments or at the RPM at the latest. It is the Investigator's responsibility to decide whether a lab value is clinically significant abnormal or not. Standard or project-specific rules for flagging clinically significant values in an automated manner will not be applied in this study.

Clinically relevant findings in laboratory data will be reported as baseline conditions (prior to first administration of study treatment) or as AEs (after first administration of study treatment) if judged clinically relevant by the investigator, and will be analyzed as such.

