1.2.2 Residual Effect Period

Based on an effective half-life of 33 h the Residual Effect Period (REP) of BI 1358894 is 11 days. This is the period after the last dose with measurable drug levels and/or pharmacodynamic effects is still likely to be present.

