	Creatinine	X	X	X
	Bilirubin, Total	X	X	X
	Bilirubin, Direct	X	X	X
	Protein, Total	X	X	X
	Albumin	X	X	X
	Albumin (Protein Electrophoresis)	X	--	--
	Alpha-1-Globulin (Protein Electrophoresis)	X	--	--
	Alpha-2-Globulin (Protein Electrophoresis)	X	--	--
	Beta-Globulin (Protein Electrophoresis)	X	--	--
	Gamma-Globulin (Protein Electrophoresis)	X	--	--
	C-Reactive Protein (Quant)	X	X	X
	Uric Acid	X	X	X
	Cholesterol, total	X	X	X
	Triglyceride	X	X	X

Proprietary confidential information © 2020 Boehringer Ingelheim International GmbH or one or more of its affiliated companies

Table 5.2.3: 1 Routine laboratory tests (cont.)

Functional lab group	BI test name [comment/abbreviation]	A	B	C
Electrolytes	Sodium Potassium Chloride Calcium Phosphate (as Phosphorus, Inorganic)	X X X X X	X X X X X	X X X X X
Urinalysis (Stix)	Urine Nitrite (qual) Urine Protein (qual) Urine Glucose (qual) Urine Ketone (qual) Urobilinogen (qual) Urine Bilirubin (qual) Urine RBC/Erythrocytes (qual) Urine WBC/Leucocytes (qual) Urine pH	X X X X X X X X X	X X X X X X X X X	X X X X X X X X X
Urine sediment (microscopic examination if erythrocytes, leukocytes nitrite or protein are abnormal in urine)	Only positive findings will be reported (for instance, the presence of sediment bacteria, casts in sediment, squamous epithelial cells, erythrocytes, leukocytes)			

A: parameters to be determined at Visit 1 (screening examination)

B: parameters to be determined on Day – 1, Day 1, Day 2, Day 7, Day 11 and Day 14 at Visits 2, 3 and 4 (for time points refer to [Flow Chart](#))

C: parameters to be determined at Visit 5 (end of trial examination)

The tests listed in Table [5.2.3: 2](#) are exclusionary laboratory tests that may be repeated as required. The results will not be entered in the CRF/database and will not be reported in the CTR. Except for drug screening, it is planned to perform these tests during screening only. Drug screening will be performed at screening and prior to each treatment period.

Table 5.2.3: 2 Exclusionary laboratory tests

Functional lab group	Test name
Drug screening (urine)	Amphetamine/MDA Barbiturates Benzodiazepine Cannabis Cocaine Methadone Methamphetamines/MDMA/XTC Opiates Phencyclidine Tricyclic antidepressants Alcohol
Infectious serology (blood)	Hepatitis A antibodies (qualitative) Hepatitis B surface antigen (qualitative) Hepatitis B core antibody (qualitative) Hepatitis C antibodies (qualitative) HIV-1 and HIV-2 antibody (qualitative)

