## 6. GENERAL ANALYSIS DEFINITIONS

### 6.1 TREATMENTS

For basic study information on treatments to be administered, assignment of treatment groups, and selection of doses, cf. Section 4 of the CTP.

The trial is divided into two parts, with the same patients included in both parts.

In **Part 1**, each subject is planned to be treated with a single oral dose (two non-radiolabelled tablets) of BI 1358894 (T1) on Day 1. Five hours after the administration of the tablet, the subjects will receive an i.v. microtracer dose of [C-14]-BI 1358894 (R1).

In **Part 2**, each subject is planned to be treated with a single oral suspension of BI 1358894 either under fasted (R2) or fed (T2) conditions on Day 1 in each period separated by a washout period of at least 17 days between the two drug administrations. The subjects will be randomly allocated to the two treatment sequences T2-R2 or R2-T2.

Single oral drug administrations of each period are separated by a washout period of at least 17 days.

Table 6.1: 1 Flow chart of analysis phases for statistical analyses of AEs

Analysis phase	Label	Start (inclusive)	End (exclusive)
Screening	Screening	Date of informed consent	Date/time of first administration of BI 1358894 in Part 1
On-treatment	BI Tab	Date/time of first administration of BI 1358894 tablet in Part 1	Date/time of start of infusion of BI 1358894 (C-14) in Part 1
On-treatment	BI Tab/C14	Date/time of start of infusion of BI 1358894 (C-14) in Part 1	Date/time of end of infusion of BI 1358894 (C-14) in Part 1 + REP (11*24h)
Follow-up	F/U BI	Date/time of end of infusion of BI 1358894 (C-14) in Part 1 + REP (11*24h)	Date/time of first administration of BI 1358894 in Part 2
On-treatment	BI fasted	Date/time of administration of BI 1358894 under fasted conditions in Part 2	Date/time of administration of BI 1358894 under fasted conditions in Part 2 + REP (11*24h)
Follow-up	F/U BI fasted	Date/time of administration of BI 1358894 under fasted conditions in Part 2 + REP (11*24h)	Date/time of administration of BI 1358894 under fed conditions in Part 2 or 12:00 a.m. on day after subject's trial termination date, whichever occurs earlier
On-treatment	BI fed	Date/time of administration of BI 1358894 under fed conditions in Part 2	Date/time of administration of BI 1358894 under fed conditions in Part 2 + REP (11*24h)

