Follow-up	F/U BI fed	Date/time of administration of BI 1358894 under fed conditions in Part 2 + REP (11*24h)	Date/time of administration of BI 1358894 under fasted conditions in Part 2 or 12:00 a.m. on day after subject's trial termination date, whichever occurs earlier

Analysis phases for statistical analysis of AEs are defined for each subject as described in the [Table 6.1: 1](#).

CTR Section 15, Appendix 16.1.13.1.8.2 and Appendix 16.1.13.1.8.3 AE displays will present results for the on-treatment phases only.

In CTR Section 15 AE tables (but not in Appendix 16.1.13.1.8.2 and Appendix 16.1.13.1.8.3 AE tables), the following totals will be provided in addition:

- "**Total BI**", defined as the total over all on-treatment phases involving BI

In disposition, demographics and baseline characteristics, all subjects will be analysed together (i.e., one "Total" column).

Safety laboratory data, vital signs and ECG will be analysed by treatment (BI, BI fasted, BI fed) with clear differentiation between baseline (cf. [Section 6.7](#)) and on-treatment measurements. Measurements will be considered on-treatment, if they were taken within the on-treatment phases as defined in Table 6.1: 1.

The following labels will be used for the comparison of treatments:

Table 6.1: 2 Overview of treatments for intra-individual comparison

Treatment	Short label
R1 100 µg BI 1358894 (C-14)	BI (C-14) 100 ug iv
T1 100 mg BI 1358894	BI 100 mg tablet
R2 100 mg BI 1358894 under fasted conditions	BI 100 mg fasted
T2 100 mg BI 1358894 under fed conditions	BI 100 mg fed

More details on the technical implementation of these analyses are provided in the ADS Plan of this TSAP.

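### The one reference-range shift table named in SAP 7.8.2 rests on the Day 11 sample, so laboratory shifts on Day 2 or Day 7 that resolve by then are not counted in it

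*SAP*

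**What the plan says.** SAP 7.8.2 plans two kinds of laboratory summary. One is descriptive statistics of values and changes from baseline over time, using a subject's worst value where several are assigned to the same planned time point. The other is a shift table: "Frequency tables of changes between baseline and last value on treatment with respect to the reference range will be presented". No any-time or worst-value shift table is named. On clinical significance the section adds: "Standard or project-specific rules for flagging clinically significant values in an automated manner will not be applied in this study".

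SAP 6.1 settles what counts as on treatment: "Measurements will be considered on-treatment, if they were taken within the on-treatment phases as defined in Table 6.1: 1". In Table 6.1: 1 the phase ends 11 x 24 h after the dose in each Part 2 period, and 11 x 24 h after the end of infusion in Part 1. The 11 days are the residual effect period of protocol 1.2.2, which is "Based on an effective half-life of 33 h".

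Protocol 5.2.3 (footnote B to Table 5.2.3: 1) gives the laboratory days in each treatment period: "parameters to be determined on Day – 1, Day 1, Day 2, Day 7, Day 11 and Day 14". The flow charts place Day 2 at 24 h, Day 7 at 144 h, Day 11 at 240 h and Day 14 at 312 h after the oral dose.

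**The concern.** A last-value table suits continuous dosing, where the last on-treatment value reflects the longest exposure. Here the oral drug is given once per period, and protocol 1.2.1 puts the fasted tablet peak at 1 to 5 h. The last value is then the on-treatment sample furthest from the peak. A subject with, say, raised ALT, CK or lipase on Day 2 and a normal result on Day 11 goes into the normal-to-normal cell.

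At stake is the count of subjects crossing a reference limit, by treatment. If a laboratory change were short-lived, the table would show little or nothing, and someone relying on it alone could conclude too readily that there was no shift. The parameters are not incidental: Appendix 10.2 of the protocol reports repeat-dose animal findings on hepatic function (mice) and on renal function and white cell parameters (mice, rats and dogs). SAP 7.8.2 also takes the worst value within a planned time point but does not carry that principle across time points into the shift table.

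**Working it through.** **1. The plan's own window.** The residual effect period divided by the effective half-life is 264 h / 33 h = 8 half-lives, exactly 11 days. The stated figure reproduces.

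**2. End of the on-treatment phase** (SAP Table 6.1: 1).
- Part 2, fasted or fed: dose + 264 h.
- Part 1: the infusion ends 5.25 h after the tablet, so the phase ends at 5.25 + 264 = 269.25 h after the tablet.

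**3. Last scheduled laboratory sample inside the phase.** Protocol 6.1 allows 120 min either way at ambulatory visits.
- Day 11: 238 to 242 h, below both 264 h and 269.25 h, so inside in every period.
- Day 14: 310 to 314 h, above both limits, so outside in every period.

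The last scheduled on-treatment value is therefore Day 11, 240 / 24 = 10 days after the oral dose. If a subject misses Day 11, an earlier sample takes its place. Days 2 and 7 otherwise do not enter the table. Nor does Day 1, whose exact laboratory time cannot be read with certainty from the flow chart as extracted; the argument does not need it.

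**4. Drug remaining at each laboratory day.** Fraction = 0.5^(t / half-life), assuming mono-exponential decline. The half-lives are 33 h (protocol 1.2.2) and the 41 to 52 h terminal half-life in Appendix 10.2.

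| Laboratory day | Time | 33 h | 41 h | 52 h |
|---|---|---|---|---|
| Day 2 | 24 h | 60% | 67% | 73% |
| Day 7 | 144 h | 4.9% | 8.8% | 14.7% |
| Day 11 | 240 h | 0.65% | 1.7% | 4.1% |

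**5. How far to trust these figures.** Protocol 1.2.1 describes a multiphasic decline with a late, low-concentration phase of about 200 h half-life, and bounds the AUC beyond 192 h only at less than 20% of the total (200 mg fed). The 33 h model would put 0.5^(192/33) = 1.8% there. That is compatible with the bound but not confirmed by it, so the model may understate late concentrations. The table is an order of magnitude, not an estimate.

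**6. What each display shows for a value that is high on Day 2 and normal at baseline and Day 11.**
- Planned shift table: normal to normal.
- Statistics by time point: contributes to the 24 h summary, and is the maximum there if it is the largest value.
- Listings: highlighted as out of range (protocol 7.3.4).
- Adverse event tables: counted only if judged clinically relevant.
- Worst-value shift table, not planned: normal to high.

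**The case against.** The strongest reply is that little is lost. The by-time-point statistics include the minimum and maximum (SAP 7) and are produced by treatment (SAP 6.1), so an extreme 24 h value shows in the correct treatment. With 12 planned subjects, highlighted listings are readable in full. Laboratory findings judged clinically relevant are tabulated as adverse events, and hepatic injury, the only event of special interest, is defined by AST, ALT and bilirubin thresholds and has its own table. No laboratory hypothesis is tested. All of this stands, and it is why the point is minor.

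Several stronger readings are tempting, but the documents do not support them:
- **That this is the only categorical laboratory display.** The adverse event and special-interest tables also count subjects with laboratory findings.
- **That the table misses the time when an effect is expected.** No section gives such a time, laboratory response need not follow plasma concentration, and Day 11 lies inside the period in which protocol 1.2.2 considers drug levels or effects still likely.
- **That under 1% of drug remains at Day 11.** This holds only for the 33 h half-life with mono-exponential decline.
- **That a 2.5-fold fed-to-fasted contrast is hidden.** That factor comes from the 100 mg food-effect part of an earlier trial. Part 2 uses a suspension and sets out to estimate the contrast, and laboratory values in both states can be compared at each time point.
- **That switching off automated flags removes reference-range checks.** The sentence concerns clinical significance; out-of-range values are still highlighted in the listings.

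SAP 7.8.2 also relies on a company standard for laboratory displays that is not available here and may add tables. What the reply does not supply is a named display that counts subjects crossing a reference limit at any on-treatment time without depending on the investigator's judgement.

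**Conclusion.** The point holds in a limited form. The one reference-range shift table named in SAP 7.8.2 uses the Day 11 (240 h) value in every period, so shifts on Day 2 or Day 7 that have resolved by then are not counted. That conclusion follows from the schedule and the phase definitions alone and does not depend on any half-life. The pharmacokinetic figures only illustrate how late Day 11 is.

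It rests on two assumptions: that Day 11 is attended, and that the unseen company standard adds no worst-value table. No endpoint, estimate or hypothesis test is affected. A reader might infer that the plan would conceal a laboratory effect. The documents do not support that, because earlier values are summarised and listed. What is missing is a convenient count by treatment.

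**What to change.** In SAP 7.8.2, keep the last-value shift table and add one of baseline against the worst on-treatment value, by treatment (BI, BI fasted, BI fed). For parameters with a two-sided range, show the highest and the lowest category separately, so that a rise and a fall in the same subject are both counted. If the company standard already produces this display, a sentence naming it is enough.

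The cost is a sentence of SAP text and one additional table from samples already scheduled. The downside is that a worst-value table draws on several samples per subject, so it will show a few more isolated out-of-range counts that need a line of explanation in the report. Keeping the last-value table beside it helps, since together they show which shifts were no longer present at the last on-treatment sample.

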### 7.8.3 Vital signs

The analyses of vital signs (blood pressure and pulse rate) will be descriptive in nature. Descriptive statistics of absolute values and change from baseline from vital signs over time (see [Section 6.7](#)) will be provided.

Unscheduled measurements of vital signs will be assigned to planned time points as follows:

- Unscheduled measurements prior to the first scheduled measurement within a visit will be assigned to the planned time point of the first scheduled measurement of that visit.
- Other unscheduled measurements will be assigned to the planned time point of the previous, most recent scheduled measurement.

Unscheduled measurements of vital signs will be used in calculation of descriptive statistics by planned time point as follows:

- If an unscheduled measurement is the last available off-treatment value before study drug administration, this unscheduled measurement will be used in the statistical analysis as baseline (as this is in accordance with the definition of baseline, cf. Section 6.7).
- At post-baseline time points, descriptive statistics by planned time point will be calculated based on the last value of the subject within 20 minutes of the scheduled measurement of that planned time point. The rationale for this rule is that these measurements are interpreted to be repeat measurements of the scheduled measurement (e.g. for confirmation of a particular value).

An unscheduled measurement more than 20 minutes after the time of the scheduled measurement of that planned time point will be listed, but will not be used in calculation of descriptive statistics. These measurements are interpreted as off-schedule vital signs measurements, taken for other reasons.

If an unscheduled measurement is taken at exactly the same time as the scheduled measurement, this unscheduled measurement will be considered to be done after the scheduled measurement, and will potentially qualify to be the “last value of the subject within 20 minutes of the scheduled measurement of that planned time point”.

If the time of measurement is missing for a scheduled measurement, the scheduled measurement will be used in calculation of descriptive statistics (as time difference between scheduled and unscheduled cannot be assessed).

If the time of measurement is missing for an unscheduled measurement, this measurement will be listed but will be ignored for the calculation of descriptive statistics.

Clinically relevant findings in vital signs data will be reported as baseline conditions (prior to first administration of study treatment) or as AEs (after first administration of study treatment) if judged clinically relevant by the investigator, and will be analyzed as such.

